### Economic Outcomes

An economic evaluation will also be performed including the costs of iliac crest bone graft harvest and complications from the bone graft surgery and the cost of the Rh-BMP 2 and the biologic implant used in the treatment group. Billing information from CMS forms UB04 and 1500 along with discharge abstracts will be obtained for treatment received by study participants at the pTOG study site hospital(s) and clinics at the end of the 12 month follow-up period. Billing records will not be collected for treatment received at hospitals or clinics not affiliated with the pTOG study. However, it will be important to document the types of treatment received so that costs for non-study site admissions and outpatient visits can be estimated during the final analysis. Therefore, during scheduled follow-up visits, patients will be asked about medical care received since the prior study visit. Responses as documented in the case report forms will provide a basis for estimating treatment costs.

### **Statistical Analyses/Data Presentation**

### Sample Size Justification

To address our primary objective, a comparison of healing rates between BMP and Autogenous Bone Grafts, we assume at 20% higher healing rate in BMP treated patients ( Jones et al, 2006), with a baseline healing rate of 65% (with autogenous bone graft). Stipulating a study power of 80% and an alpha level=0.05, and a non-inferiority margin of 20% our study will require at least 14 patients per treatment arm. If we stipulate our non-inferiority margin to be 10%, we will require 25 patients per group. Thus, to be most conservative, our study will recruit 50 patients total (25 patients per treatment arm). We will complete an interim evaluation of results once 25 patients have been enrolled, including a power analysis.

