## **IRB00003098 Funding Protocol rhBMP-2/ACS vs. Autograft for Critical Size Tibial Defects**

*Null hypothesis: rhBMP-2/ACS has the same union rate when used in critical-sized defects as does ICBG.*

*Secondary:*

What is the relative effect of rhBMP-2 versus autogenous ICBG on infection rates in patients with nonunion or critical size defects following tibial shaft fractures?

*Null hypothesis #2: The infection rate in open tibias with critical-sized defects treated with rhBMP-2 and autogenous ICBG are the same.*

What is the economic impact of the use of RhBMP 2 for tibial fractures with critical sized defects?

*Null hypothesis #3: There will be no difference in the economic cost of the treatment of critical sized defects using the RhBMP-2 versus iliac crest bone graft.*

This investigation is a prospective, stratified, parallel, randomized, blinded multicenter trial to evaluate the use of rhBMP-2/ACS in 25 patients versus a control group of 25 patients who have tibial fractures with critical size defects. A committee of orthopaedic surgeons will independently adjudicate our primary outcome, fracture healing at 12 months. Participating centers are part of the Major Extremity Research Consortium (METRC) and have experience with performing randomized clinical trials. Approval by each center's institutional review board will be obtained prior to commencing the study and we will follow the research guidelines set forth by each site.

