### Final Analysis

The results will be reported comparing the outcomes in the groups at each follow-up period. It is anticipated that the required patients will be entered into the investigation during an 18-month period and will be followed for one year. Thus, the data collection time will be a 2.5- year period. We believe that at that time, the results of the study will reveal whether any differences exist with this high-energy disabling fracture in terms of outcomes, union rates, times to union, soft-tissue complications and infection rates.

Data will be analyzed on an intent to treat basis (patient data included in the treatment group and stratum to which randomized). Fishers exact test will be used to compare categorical variable and the Student t test will be used for continuous variables for comparisons between the two groups.

Quality of life data will be coded and scored according to the guidelines provided with the SMFA (Coding Key Manual, Musculoskeletal Function Assessment, Injury and Arthritis Survey) and the SF-12 (Coding Manual for the SF-12 Health Survey).

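### The 25 per arm and 80% power come from a non-inferiority margin, but the stated null is equal union rates and the only test named for such an outcome, Fisher's exact test, ignores the margin and has 25% (two-sided) or 39% (one-sided) power at the plan's assumed rates

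*Combined protocol and SAP*

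**What the plan says.** Three parts of the protocol bear on the primary comparison.

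- **Sample Size Justification.** The autograft healing rate is taken as 65%, and for BMP "we assume at 20% higher healing rate in BMP treated patients". The calculation opens with "Stipulating a study power of 80% and an alpha level=0.05, and a non-inferiority margin of 20" percent, which leads to 14 per arm. It continues: "If we stipulate our non-inferiority margin to be 10%, we will require 25 patients per group". The trial then recruits 25 per arm, which in effect adopts the 10-point margin. Alpha is not said to be one- or two-sided.
- **Research Question.** The primary null hypothesis is that "rhBMP-2/ACS has the same union rate when used in critical-sized defects as does ICBG". It contains no margin.
- **Final Analysis.** The stated expectation is that "the results of the study will reveal whether any differences exist". The method is one general line: "Fishers exact test will be used to compare categorical variable and the Student t test will be used for continuous variables". Union at 12 months is binary, so Fisher's test is the one that applies. Its sidedness is not stated.

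The margin appears only in the Sample Size Justification. I found no non-inferiority hypothesis, no confidence bound to be compared with a margin, and no rule for concluding non-inferiority.

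**The concern.** The sample size belongs to a non-inferiority trial, while the hypothesis and the test belong to a trial looking for a difference. Three things follow.

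- The 80% power does not describe the test that would be run.
- The most likely result under the plan's own assumptions is a non-significant Fisher p-value. That shows neither superiority nor non-inferiority. Because the protocol uses non-inferiority language, a reader could take it to mean that BMP is as good as autograft, although the test would usually be non-significant even if BMP were much worse.
- The plan could miss a non-inferiority conclusion that the data support, because nothing in the analysis compares the result with the margin. Without a fixed hypothesis and sidedness, the decision rule could also be settled after the data are seen.

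**Working it through.** **Inputs.** From the Sample Size Justification: autograft 65%, BMP 20% higher, power 80%, alpha 0.05, margins of 20 and 10 points, 25 per arm. From the Research Question: a null of equality. From the Final Analysis: Fisher's exact test. Two readings are inferred because the text leaves them open: one-sided alpha, and 20% as an absolute difference (85% v 65%).

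**1. Reproducing the plan's sizes.** Per arm, with the unpooled normal approximation:

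n = (z_alpha + z_beta)² × [0.65×0.35 + 0.85×0.15] / (0.20 + margin)²

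The bracket is 0.2275 + 0.1275 = 0.355. At one-sided 0.05, (1.645 + 0.842)² = 6.18.

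- Margin 20 points: 6.18 × 0.355 / 0.16 = 13.7, so 14.
- Margin 10 points: 6.18 × 0.355 / 0.09 = 24.4, so 25.

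Both match. The alternative readings do not:

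| Reading | Margin 20 | Margin 10 |
|---|---|---|
| 85% v 65%, one-sided 0.05 | 14 | 25 |
| 85% v 65%, one-sided 0.025 (two-sided 0.05) | 18 | 31 |
| 78% v 65% (0.65 × 1.20, relative reading), one-sided 0.05 | 23 | 47 |

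**2. Power of Fisher's test at 25 per arm.** I enumerated all 26 × 26 possible outcomes, weighted them by their binomial probabilities, and counted rejection when p ≤ 0.05.

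- 85% v 65%: 25.3% two-sided, 38.8% one-sided.
- 65% v 65%: two-sided type I error 2.6%.
- 45% v 65% (BMP 20 points worse): two-sided non-significant 76.4% of the time.
- Single example: autograft 16/25 and BMP 9/25, a deficit of 7/25 = 28 points, gives two-sided p = 0.089.

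Fisher's conservatism is not the main cause. A pooled z-test, by normal approximation, has 36.8% power two-sided or 49.5% one-sided at 85% v 65%.

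**3. Power of a test that does use the margin.** Farrington-Manning score test, 10-point margin, 25 per arm, by the same enumeration:

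| True BMP rate (autograft 65%) | One-sided 0.05 | One-sided 0.025 |
|---|---|---|
| 85% | 80.7% | 69.9% |
| 78% | 57.0% | – |
| 65% | 17.7% | – |

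If the arms are truly equal, 80% power at one-sided 0.05 needs 6.18 × (2 × 0.2275) / 0.10² = 281.3, so 282 per arm (unrounded z-values).

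**4. How often the two analyses part.** At 85% v 65%, 55% of trials would have a non-significant two-sided Fisher test while the score test (one-sided 0.05) shows non-inferiority at 10 points.

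**5. Size for 80% power to detect a difference.** At 85% v 65% and two-sided 0.05, the pooled normal formula gives

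[1.960 × √(2×0.75×0.25) + 0.842 × √0.355]² / 0.20² = 72.4, so 73 per arm.

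Exact enumeration for Fisher's test gives 79.9% at 80 per arm and 80.15% at 81, so about 81 per arm.

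**The case against.** The strongest reply is that the sample size is correct for the question it was computed for. The 14 and 25 reproduce exactly, and setting 25% against 80% compares power for two different hypotheses. The Fisher line is general and is never labelled the primary test, so one could say the non-inferiority analysis is merely unspecified. No sentence says that a non-significant p-value will be read as equivalence, and the scenario with BMP worse runs against the plan's own assumption. The figures at 78% and 65% concern the assumed benefit more than the mismatch.

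Part of this stands. That Fisher's test is the test for union is an inference, as are one-sided alpha and the 10-point margin. The misreading is a risk and not a stated intention. The 78% and 65% figures matter because power must be restated once the margin is used; they are not what makes the plan inconsistent.

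It does not rescue the plan. The written null is equality, so non-inferiority is not simply implied, and no other test for a binary outcome is given.

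The remedy also has limits. The score test is approximate: at 25 per arm its type I error is 4.5% at 55% v 65%, but it can exceed 5% at some other control rates. The 81% assumes that all 50 are evaluable at 12 months, that observations are independent although both tibias of one patient may be randomised, and that no alpha is spent at the planned interim evaluation.

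**Conclusion.** The concern holds and should be fixed before the analysis. The stated 80% power belongs to a 10-point non-inferiority comparison that the plan neither states as a hypothesis nor tests. For the stated hypothesis and the named test, power at 25 per arm is 25% two-sided or 39% one-sided. These figures rest on true rates of 85% and 65% and alpha 0.05. The absolute reading of the 20% benefit is supported by the match at both margins. Under the relative reading (78%), Fisher's power is lower still: 10.1% two-sided and 17.9% one-sided.

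**What to change.** Make the hypothesis, test and power figure match, and state the sidedness. There are two ways.

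**A. Non-inferiority, which fits the existing size.**
- State the null as union(BMP) minus union(ICBG) ≤ −10 points, with one-sided alpha 0.05. The sponsor must choose and justify both the margin and the alpha; at one-sided 0.025, power falls to about 70%.
- Make the primary analysis a score-based lower confidence bound for the difference (for example Miettinen-Nurminen or Farrington-Manning). Conclude non-inferiority only if the bound lies above −10 points.
- Keep Fisher's test for other categorical outcomes, or for superiority once non-inferiority is met.
- Restate power as about 81% if BMP is truly 20 points better, about 57% at a BMP rate of 78%, and about 18% if the arms are equal. Calling the design most conservative can stay as a comparison of the two margins, but add that the size depends on the assumed 20-point BMP advantage, and give the assumptions on evaluability, independence and interim alpha.

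Cost: protocol wording and a less favourable power statement; no extra patients.

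**B. Difference.**
- Keep the equality null and Fisher's test, and remove the margin.
- Either restate power as about 25% (two-sided) or re-size.
- State that a non-significant result will not be read as non-inferiority.

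Cost: wording only if 25% power is accepted; about 81 per arm in place of 25 if 80% is to be kept.

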### Final Analysis

The results will be reported comparing the outcomes in the groups at each follow-up period. It is anticipated that the required patients will be entered into the investigation during an 18-month period and will be followed for one year. Thus, the data collection time will be a 2.5- year period. We believe that at that time, the results of the study will reveal whether any differences exist with this high-energy disabling fracture in terms of outcomes, union rates, times to union, soft-tissue complications and infection rates.

Data will be analyzed on an intent to treat basis (patient data included in the treatment group and stratum to which randomized). Fishers exact test will be used to compare categorical variable and the Student t test will be used for continuous variables for comparisons between the two groups.

Quality of life data will be coded and scored according to the guidelines provided with the SMFA (Coding Key Manual, Musculoskeletal Function Assessment, Injury and Arthritis Survey) and the SF-12 (Coding Manual for the SF-12 Health Survey).

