The purpose of our study is to evaluate the use of one such recombinant protein in patients at a high risk for nonunion. We will evaluate open tibial shaft fractures treated with an intramedullary nail and a circumferential bone defect of at least one centimeter in length compromising at least 50% of the circumference of the bone. Patients with critical sized defects who undergo a planned, secondary grafting or whose fractures fail to demonstrate progression towards union over three consecutive months of radiographic and clinical evaluation will be included. Patients will be randomized to the use of recombinant human bone morphogenetic protein 2 (RhBMP-2) or standard ICBG to stimulate healing. The ability to restore skeletal integrity without the morbidity associated with bone graft harvesting would represent a major advantage for the patient. As a secondary evaluation, given that rhBMP-2 has been associated with decreased infections when used in open tibia fractures, we will also determine if patients with these severe fractures have a decreased infection rate with the use of rhBMP-2/ACS relative to the control group. In addition, the overall economic impact of the 2 treatment groups will be evaluated with a cost effectiveness evaluation.

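### Infection is to be compared by Fisher's exact test alone, with no effect estimate or interval; at 25 per arm that says little about whether rhBMP-2 lowers infection, and a better summary costs almost nothing

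*Combined protocol and SAP*

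**What the plan says.** Infection is the first-listed secondary question. The Purpose section, in a sentence that introduces infection as a secondary evaluation, says that "we will also determine if patients with these severe fractures have a decreased infection rate with the use of rhBMP-2/ACS" relative to control. The second null hypothesis, listed with the secondary research questions, reads "The infection rate in open tibias with critical-sized defects treated with rhBMP-2 and autogenous ICBG are the same".

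Final Analysis expresses the belief that the results will reveal "whether any differences exist with this high-energy disabling fracture in terms of outcomes, union rates, times to union, soft-tissue complications and infection rates". It assigns Fisher's exact test to categorical variables and the t test to continuous ones. It names no effect measure and no confidence interval.

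Sample Size Justification concerns healing only. Its inputs are "we assume at 20% higher healing rate in BMP treated patients" and a control rate given as "with a baseline healing rate of 65% (with autogenous bone graft"; on the smaller margin it says "If we stipulate our non-inferiority margin to be 10%, we will require 25 patients per group". The combined document gives no expected infection rate, detectable difference, margin, power or test sidedness for infection.

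**The concern.** A stated aim to determine whether infection falls is paired with an analysis that returns only a p-value, in a trial sized for another outcome. Infections are counts out of 25 per arm. At such counts Fisher's test is strongly conservative, so part of the 5% error allowance goes unused.

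Infection bears on both benefit and safety: Purpose raises a possible reduction, and Wound Complications defines deep and superficial infection in detail. If the only planned output is a p-value and it is not significant, a reader cannot tell a true absence of effect from a large effect that was missed. An interval would show the difference.

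**Working it through.** **Inputs from the documents.** 25 patients per arm and alpha 0.05, both from Sample Size Justification (the alpha is given there for healing); Fisher's exact test, from Final Analysis. **Assumptions.** Infection rates, because the documents give none, so a range is shown; all 25 per arm with a known infection outcome; two-sided 5% unless stated otherwise.

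**1. The plan's own sample size.** For healing, n per arm = (z for alpha + z for power)² × [p₁(1−p₁) + p₂(1−p₂)] / (difference + margin)².
- Variance term: 0.65×0.35 + 0.85×0.15 = 0.355.
- One-sided 0.05, 80% power: (1.645 + 0.842)² = 6.18.
- Margin 10 points: 6.18×0.355/0.30² = 24.4, so 25. Margin 20 points: 6.18×0.355/0.40² = 13.7, so 14.

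Both figures reproduce. With one-sided 0.025 they would be 31 and 18, so the alpha used for healing is one-sided 0.05. None of this speaks to infection.

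**2. What Fisher needs to reject.** With no infections on rhBMP-2 and k on control, the two-sided p-value is 2 × C(25,k)/C(50,k).
- k = 5: 2 × 53,130/2,118,760 = 0.0502, not rejected.
- k = 6: 2 × 177,100/15,890,700 = 0.0223, rejected.

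| rhBMP-2 infections | Fewest control infections to reject | p |
|---|---|---|
| 0 | 6 (24%) | 0.022 |
| 1 | 7 (28%) | 0.049 |
| 2 | 9 (36%) | 0.037 |
| 3 | 11 (44%) | 0.025 |

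The first row is fragile. At 24 per arm, 0 v 5 gives 2 × 42,504/1,712,304 = 0.0496 and rejects. At 25 per arm with a one-sided 5% test, 0 v 5 gives p = 0.025 and rejects.

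**3. True error rate and power.** These come from full enumeration of the 26 × 26 possible outcomes: the sum, over rejected pairs (i, j), of Bin(i; 25, p_T) × Bin(j; 25, p_C).
- Fisher's true two-sided size is 0.9% at a common rate of 10% and 2.2% at 20%. Its maximum over all common rates is 3.3%.
- Boschloo's unconditional exact test uses the Fisher p-value as its statistic, with a critical value of about 0.079. Its maximum size is 4.6%. It rejects wherever Fisher does, and also at 0 v 5, 2 v 8 and 3 v 10.

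| Control v rhBMP-2 rate (assumed) | Fisher, two-sided | Boschloo, two-sided | Fisher, one-sided 5% |
|---|---|---|---|
| 20% v 10% | 9% | 12% | 16% |
| 20% v 5% | 20% | 27% | 33% |
| 30% v 10% | 31% | 39% | 45% |

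If rhBMP-2 halves the infection rate, two-sided Fisher power is 1%, 9%, 15% and 23% at control rates of 10%, 20%, 30% and 40%. If rhBMP-2 abolished infection, 80% power would need a true control rate of about 30%. For scale, 80% power for 20% v 10% (two-sided 5%, normal approximation) takes 199 per arm.

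**4. What a null result leaves open (Newcombe 95% intervals, rhBMP-2 minus control).**
- 3 v 3: −20 to +20 points.
- 5 v 5: −22 to +22 points.
- 2 v 5 (p = 0.42): −32 to +8 points.

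**The case against.** **Infection is secondary, and low power for a secondary outcome is normal.** This stands. The trial is sized for healing, no power is claimed for infection, and nothing here asks for more patients. What remains is that no estimate or interval is planned for a question the plan says it will settle.

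**A reader might infer that the plan intends to report equal infection rates if the test is not significant.** The documents do not support that. The sentence "The infection rate in open tibias with critical-sized defects treated with rhBMP-2 and autogenous ICBG are the same" is labelled a null hypothesis and is ordinary null wording, and nowhere does the plan say that non-rejection will be read as equality. Nor can a non-significant superiority test show equality at any sample size, so this is not peculiar to Fisher or to 25 per arm.

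**A reader might infer that the plan guarantees an answer on infection.** Final Analysis states a belief, not a guarantee. Only *determine* in Purpose is unqualified, and even that sentence calls infection a secondary evaluation.

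**The 0 v 6 threshold depends on choices the plan does not make.** This also stands. Sidedness is not stated; Purpose is directional, while the null and Final Analysis are not. One-sided testing or one fewer patient per arm brings the cut-off to 5. The larger result, low power at plausible rates, survives both.

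**Fisher's test is valid, and replacing it rescues little.** Correct. Fisher controls type I error. Boschloo adds 3 to 8 percentage points of power in the scenarios tabulated, less than a one-sided Fisher test would add, so settling sidedness matters more than choosing the test. The interval is the main remedy.

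**Conclusion.** The point holds as an improvement to the analysis, not as an error in a stated figure. With 25 per arm, a two-sided Fisher test has 1% to 23% power to detect a halving of infection across assumed control rates of 10% to 40%. Non-rejection would therefore occur 77% to 99% of the time even if the effect were real. It would be too strong to call a null result close to certain across that whole range.

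A non-significant p-value leaves differences of about 20 points open, and the plan as written would not display that. Fisher's true error rate of about 1% to 2% at infection rates of 10% to 20% means a more powerful exact test is available for the same patients, though the comparison would still be poorly powered. The figures rest on assumed infection rates, complete infection outcomes and, except where marked, two-sided testing. The primary healing analysis is unaffected.

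**What to change.** 1. In Final Analysis, make the risk difference with a 95% confidence interval (Newcombe or exact) the main infection result.
2. In the same place, state whether the infection test is one-sided or two-sided.
3. If a p-value is kept for infection, use Boschloo's unconditional exact test. It never rejects less often than Fisher and keeps the error rate at or below 5%. Add that the comparison remains imprecise.
4. In Purpose, replace *determine* with *estimate* for infection, and say that a non-significant result will not be read as equal infection rates.

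The cost is a few sentences, a test less familiar to clinical readers, and a less favourable claim about what the trial can show. No additional patients, visits or data are needed. The change should be made before outcome data are seen by treatment group.

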### Duration/Follow-up Schedule

It is anticipated that the required patients will be enrolled into this study during an 18-month period and will be followed for one year. Thus, the data collection time is anticipated to be a 2.5 year period. The patients will be evaluated at 2 weeks, 6 weeks, 12 weeks, 18 weeks, 6 months and 12 months according to the following schedule:

Follow-Up Schedule	Process	Data Collected
Enrollment	Clinical examination	Inclusion/Exclusion criteria, patient characteristics, fracture characteristics, surgical summary, VAS
2 weeks	Clinical examination, functional outcomes	Clinical follow-up data, VAS
6 weeks	Clinical examination, functional outcomes, radiographs	Clinical follow-up data, VAS
12 weeks	Clinical examination, functional outcomes, radiographs	Clinical follow-up data, VAS
18 weeks	Clinical examination, functional outcomes, radiographs	Clinical follow-up data, VAS
6 months	Clinical examination, functional outcomes, radiographs	Clinical follow-up data, VAS, SF12, SMFA
12 months	Clinical examination, functional outcomes, radiographs	Clinical follow-up data, VAS, SF12, SMFA

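### Times to union are a named result, but the only stated method that fits a time is the Student t test, and no rule covers patients who do not unite

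*Combined protocol and SAP*

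**What the plan says.** The Final Analysis section lists what the study should reveal between the groups: "union rates, times to union, soft-tissue complications and infection rates". It names two tests. For categorical outcomes, "Fishers exact test will be used to compare categorical variable"; otherwise "the Student t test will be used for continuous variables for comparisons between the two groups". It also states "Data will be analyzed on an intent to treat basis". No section available for review gives a time-to-event method, a start point for time to union, or a rule for patients who have not united, are lost, or are re-grafted.

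Sample Size Justification assumes that many patients will not heal: it works "with a baseline healing rate of 65% (with autogenous bone graft") and says "we assume at 20% higher healing rate in BMP treated patients". Under Duration/Follow-up Schedule, "The patients will be evaluated at 2 weeks, 6 weeks, 12 weeks, 18 weeks, 6 months and 12 months". The table there shows radiographs from the 6-week visit onward. The Retrieval Study section foresees a salvage autograft after failure with rhBMP-2.

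**The concern.** A patient who has not united by 12 months has no union time. A t test must therefore either leave that patient out or use a time that was not observed. Leaving failures out makes the comparison depend on the outcome, so the groups compared are no longer the randomised groups. An arm that converts failures into late unions can then show a longer mean time although it heals more patients and delays none.

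Speed of healing is a claim the trial could be used to support: the Steps to Minimize Risk section describes possible patient benefits if rhBMP-2 accelerates healing. The results also come on a coarse grid. Any union after 6 months is first seen at the 12-month visit.

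**Working it through.** **Inputs from the plan.** 25 patients per arm; healing 65% (autograft) and 65% + 20 points = 85% (rhBMP-2); radiograph visits at 6, 12, 18, 26 and 52 weeks, taking 6 and 12 months as 26 and 52 weeks.

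**The plan's own figure.** To confirm that the 20% means points, use n per arm = (z₀.₉₅ + z₀.₈₀)² × [p₀(1−p₀) + p₁(1−p₁)] / (difference + margin)². The numerator is (1.645 + 0.842)² × (0.2275 + 0.1275) = 2.195.
- Margin 20 points: 2.195 / 0.40² = 13.7, so 14.
- Margin 10 points: 2.195 / 0.30² = 24.4, so 25.

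Both match the plan at one-sided 0.05, so 65% v 85% is the right reading.

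**Who has a union time.** Autograft: 25 × 0.65 = 16.25. rhBMP-2: 25 × 0.85 = 21.25. Without a time: 8.75 + 3.75 = 12.5 of 50, that is 35% v 15% by arm.

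**Scenario 1: unions spread over the year (assumed Weibull times, shape 1 to 2, reaching 65% v 85% at 52 weeks).** For shape 1 the rates are −ln(0.35)/52 = 0.0202 and −ln(0.15)/52 = 0.0365 per week. The proportions first seen united at weeks 6, 12, 18, 26 and 52 are:
- autograft: 0.1141, 0.1011, 0.0895, 0.1037, 0.2416; united-only mean 18.77 / 0.65 = 28.9 weeks
- rhBMP-2: 0.1966, 0.1579, 0.1269, 0.1313, 0.2373; united-only mean 21.11 / 0.85 = 24.8 weeks

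The mean points the right way. In simulation (2,000 or more trials per scenario, 25 per arm, two-sided 0.05), over the three shapes:
- united-only t test: about 8–10% power; rhBMP-2 looks slower in about 25–28% of trials, significantly so in under 1%
- log-rank on all patients, failures censored at 52 weeks: about 40–43%
- Fisher's test on 12-month union: about 25%

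**Scenario 2: the extra unions are all late (assumed).** Early unions are 45% in both arms, with mean recorded time m; late unions, all recorded at 52 weeks, are 20% v 40%. Take m = 15 (early unions split evenly between the 12- and 18-week visits).
- Autograft: (0.45 × 15 + 0.20 × 52) / 0.65 = 17.15 / 0.65 = 26.4 weeks
- rhBMP-2: (0.45 × 15 + 0.40 × 52) / 0.85 = 27.55 / 0.85 = 32.4 weeks

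rhBMP-2 appears about 6 weeks slower, although it heals 20 points more patients and has the same early unions. In simulation it looks slower in about 84% of trials. The t test is significant against it in about 16% and for it in about 0.2%; log-rank is significant for it in about 17% and against it in about 0.3%.

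**Assigning 52 weeks to failures.** In scenario 2 the late unions and the failures then share one value. The mean is 0.45 × 15 + 0.55 × 52 = 35.35 weeks in both arms, a difference of exactly 0. Where unions come earlier this rule does less harm, but it still treats a censored time as observed.

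**How much of the log-rank gain concerns timing.** If union times among united patients have the same distribution in both arms, log-rank still rejects in favour of rhBMP-2 in about 30% of trials, purely from the union-rate difference. The t test does so in 2.5%.

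**The case against.** **The plan never says that time to union gets a t test.** This is correct. The phrase stands in a sentence of expectation, and time to union is absent from the research questions and from the lists of outcome measures. A reader might infer that the sponsor has prescribed a t test on united patients. The documents support only that no other named method fits a time and that no rule for failures is given.

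**Timing may be covered without selection.** The Final Analysis section opens by saying that outcomes will be compared at each follow-up. With Fisher's test and intent to treat, that gives the proportion united at each visit with failures included. This is a fair reading and softens the point, but it does not supply a method for times to union.

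**Reversal needs a particular pattern.** A reader might infer that the worse arm will generally look better. It does not in scenario 1; it does in scenario 2, which is an assumption. Even there most trials are not significant, and log-rank power (about 17%) is below that of Fisher's test on 12-month union (about 25%). Log-rank is therefore not a powerful remedy in that case; its merit is that it rarely points the wrong way.

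**The power gap mixes two questions.** This also stands. About 9% v 41% should not be read as pure loss of information on speed, because log-rank also picks up the union-rate difference.

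**Conclusion.** The gap is real and of moderate weight. Followed as written, the plan leaves about a quarter of patients, unequally by arm (35% v 15%), outside any t test of time to union, or gives them an arbitrary value. The first conflicts with the intent-to-treat statement; the second can hide a true difference.

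The counts rest on the plan's own rates. The power and reversal figures rest on assumed time distributions and show what can happen, not what will. A reader might also infer that the main conclusion of the trial is at risk. It is not: the primary outcome, healing at 12 months, is binary and can be tested in all patients, and the infection and cost questions are untouched.

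**What to change.** Take time to union out of the t-test sentence and state that:
- it is analysed in all randomised patients, by Kaplan-Meier curves and a log-rank test on visit times, or by an interval-censored model using the last non-united and first united visits;
- patients not united are censored at their last assessment;
- the time origin is defined, including for anyone randomised but not grafted, since the Consent Procedures and the exclusion criteria allow exclusion at surgery;
- a patient re-grafted before union counts as not united on the assigned treatment through 12 months, or re-grafting is a competing event. Such a patient should not be censored at re-graft, which would be informative, or credited with a later union, which would belong to the salvage graft.

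The cost is a short paragraph, a little more analysis work and one pre-specified rule for re-grafted patients. The scheduled visits already collect the data.
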